# 9.1. Analysis of Primary Efficacy Endpoint

The primary efficacy endpoint is the time to treatment success, where such time (in days) is defined as from initiation of study drug to when a cell count of 0 is achieved and maintained (without cell count increase to > 0) to Week 4 without being rescued (or discontinued due to the requirement for rescue therapy) at any time prior to Week 4. All rescued subjects and subjects who did not achieve treatment success will be right censored. Subjects who discontinue from the study for reasons other than rescue will be real-time censored. Event and censoring definitions are described in Table 4 below.

The primary analysis to test superiority of ADX-102 over vehicle is the stratified log-rank test, stratified for the baseline ACC grade, with missing data imputed using the last observation carried forward (LOCF) approach. The Kaplan-Meier method (Kaplan and Meier 1958) will be used to estimate the time to treatment success curve. The Cox proportional hazards model with treatment group as a factor, stratified by the baseline ACC grade, will be used to estimate the hazard ratio and corresponding 95% confidence interval.

Table 4: Event and Censoring for Time to Treatment Success Analysis

Situation	Event / Censored	Date of Event / Censoring
Treatment success	Event	Date when the first cell count of 0 is achieved prior to or at Week 4 and maintained (without cell count increase to > 0) to Week 4 without being rescued any time prior to Week 4
Cell count greater than 0 at Week 4	Censored	Date of Week 4
Rescued	Censored	Date of Week 4
Early discontinuation from study for reasons other than rescue	Censored	Date of study discontinuation or Week 4, whichever is the earlier

#### Sensitivity Analyses

The following sensitivity analyses will be conducted to evaluate the robustness of the result from the primary analysis:

- 1) *Unstratified Analysis:* An unstratified log-rank test on the ITT population with missing data imputed by the LOCF approach. The unadjusted hazard ratio and 95% CI will be estimated from Cox model.
- 2) Best Within-Subject Observation: A stratified log-rank test on the ITT population with missing data imputed by the within-subject best observation from Day 1 to Week 4 or Early Termination. The hazard ratio and 95% CI will be estimated from Cox model stratified for the baseline ACC grade.
- 3) Worst Within-Subject Observation: A stratified log-rank test on the ITT population with missing data imputed by the within-subject worst observation from Day 1 to Week 4 or Early Termination. The hazard ratio and 95% CI will be estimated from Cox model stratified for the baseline ACC grade
- 4) Subjects with Unscheduled Visits: A stratified log-rank test on the ITT population with missing data imputed by the LOCF approach. Values from scheduled and unscheduled visits will be pooled before imputation. The hazard ratio and 95% CI will be estimated from Cox model, stratified for the baseline ACC grade

Throughout this Statistical Analysis Plan, rescue will be defined as disease worsening or lack of disease improvement that, at the discretion of the investigator, requires rescue therapy. Prior to database lock, discontinued subjects will be adjudicated as to whether the discontinuation was primarily due to the requirement of rescue therapy.

# 9.2. Analysis of Secondary Efficacy Endpoints

#### 9.2.1. Time to Cell Grade Reduction

The time to cell grade reduction is defined as the time (in days) from initiation of study drug to the date that improvement (decrease) from baseline in ACC grade of at least 1 grade was achieved without being rescued (or discontinued due to the requirement for rescue therapy) at any time prior to Week 4. All rescued subjects and subjects who did not achieve treatment success will be right censored. Subjects who discontinue from the study for reasons other than rescue will be real-time censored. Event and censoring definitions are described in Table 5 below.

Missing ACC grade will be imputed using the LOCF approach. A log-rank test stratified by the baseline ACC grade will be performed for between-group comparison. The Kaplan-Meier plot will be generated. The Cox proportional hazards model, with treatment group as a factor and

stratified by the baseline ACC grade, will be used to estimate the hazard ratio and corresponding 95% confidence interval.

Table 5: Event and Censoring for Time to Cell Grade Reduction Analysis

Situation	Event / Censored	Date of Event / Censoring
Cell grade reduction	Event	Date when the first ACC grade with at least 1 grade decrease from baseline was achieved without being rescued at any time prior to Week 4
Cell grade reduction does not meet 1 grade reduction from baseline prior to or at Week 4	Censored	Date of Week 4
Rescued	Censored	Date of Week 4
Early discontinuation from study for reasons other than rescue	Censored	Date of study discontinuation or Week 4, whichever is the earlier

## 9.2.2. Time to Flare Treatment Success

The time to flare treatment success is defined as the time (in days) from initiation of study drug to the date that the anterior chamber flare grade reached 0 and maintained (without flare grade increase to > 0) to Week 4 without being rescued (or discontinued due to the requirement for rescue therapy) at any time prior to Week 4. All rescued subjects and subjects who did not achieve treatment success will be right censored. Subjects who discontinue from the study for reasons other than rescue will be real-time censored. Event and censoring definitions are described in Table 6 below.

Missing anterior chamber flare grade will be imputed using the LOCF approach. A log-rank test will be performed for between group comparison. The Kaplan-Meier plot will be generated. The Cox proportional hazards model with treatment group as a factor will be used to estimate the hazard ratio and corresponding 95% confidence interval.

Table 6: Event and Censoring for Time to Flare Treatment Success Analysis

Situation	Event / Censored	Date of Event / Censoring
Flare treatment success	Event	Date when the first anterior chamber flare grade of 0 is achieved prior to or at Week 4 and maintained (without flare grade increase to > 0) to Week 4 without being rescued any time prior to Week 4
Anterior chamber flare grade greater than 0 at Week 4	Censored	Date of Week 4
Rescued	Censored	Date of Week 4
Early discontinuation from study for reasons other than rescue	Censored	Date of study discontinuation or Week 4, whichever is the earlier

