# 3.2. Statistical Analysis Issues

#### 3.2.1. Strata and Covariates

The randomization of the study is stratified based on baseline ACC grade: 1+, 2+, 3+ in the study eye (SAP Section 3.2.7). For time to efficacy endpoints, a stratified log-rank test to test treatment effect stratified by the baseline ACC grade used for randomization stratification will be performed. Stratified Cox proportional hazards regression model will also be performed.

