# 9. EFFICACY ANALYSES

All of the efficacy analyses will be performed on the ITT analysis set. The PP analysis set will be used as supportive analyses for the primary and secondary efficacy endpoints. Unless otherwise noted, unscheduled and early termination visits will be assigned to an unplanned study visit using the analysis windows described in SAP Section 3.2.9 (Table 3) in case the scheduled visit was not performed.

Although it is possible for the subjects who are experiencing a bilateral episode of anterior uveitis be treated in both eyes, the study eye will be used as the primary eye in the efficacy analyses. The definition of the study eye is described in SAP Section 3.2.7. Summary of descriptive statistics will be presented for all study visits at which efficacy data were collected. In addition, descriptive statistics summary will be performed separately on the study eye and on the non-study eye where it is applicable.

For the time to event data, Kaplan-Meier method and Cox proportional hazards regression model will be used for the analysis. Descriptive summary [n (%) subjects with event, n (%) subjects censored without event, median, 25th and 75th percentiles] by treatment group. Stratified and unstratified log-rank test will be used for the treatment group comparison. The stratified analysis based on the baseline ACC grade used for randomization stratification will be the primary method.

For the categorical data, stratified Cochran-Mantel-Haenszel (CMH) test and/or Fisher's exact test will be used for the treatment group comparison. If both stratified CMH and Fisher's tests are used, the stratified CMH test will be the primary method.

Non-primary or secondary efficacy endpoints will be summarized for descriptive statistics only. No statistical treatment group comparison will be performed.

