#### 9.2.3. Time to Flare Grade Reduction

The time to flare grade reduction is the time (in days) from initiation of study drug to the date that improvement (decrease) in anterior chamber flare grade of at least 1 unit was reached without being rescued (or discontinued due to the requirement for rescue therapy) at any time prior to Week 4. All rescued subjects and subjects who did not achieve treatment success will be right censored. Subjects who discontinue from the study for reasons other than rescue will be real-time censored. Event and censoring definitions are described in Table 7 below.

Missing anterior chamber flare grade will be imputed using the LOCF approach. A log-rank test will be performed for between group comparison. The Kaplan-Meier plot will be generated. Cox proportional hazards model with treatment group as a factor will be used to estimate the hazard ratio and corresponding 95% confidence interval.

Table 7: Event and Censoring for Time to Flare Grade Reduction Analysis

Situation	Event / Censored	Date of Event / Censoring
Flare grade reduction	Event	Date when the first AC flare grade with at least 1 grade decrease was achieved prior to Week 4 without being rescued at any time prior to Week 4
Flare grade reduction does not meet 1 grade reduction from baseline prior to or at Week 4	Censored	Date of Week 4
Rescued	Censored	Date of Week 4
Early discontinuation from study for reasons other than rescue	Censored	Date of study discontinuation or Week 4, whichever is the earlier

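### Do the flare endpoints lose their stratified analysis because SAP 9.2.2 and 9.2.3 do not name the stratum?

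*SAP*

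**What the plan says.** Two general rules in the SAP cover time-to-event efficacy endpoints.

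- Section 3.2.1 calls for "a stratified log-rank test to test treatment effect stratified by the baseline ACC grade used for randomization stratification" and then says "Stratified Cox proportional hazards regression model will also be performed".
- Section 9, before any endpoint is taken up, says "Stratified and unstratified log-rank test will be used for the treatment group comparison" and ranks the two: "The stratified analysis based on the baseline ACC grade used for randomization stratification will be the primary method". For categorical endpoints it ranks in the same way: if CMH and Fisher are both used, "the stratified CMH test will be the primary method".

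The endpoint sections then describe each analysis. Section 9.1 names the stratum in full: "The primary analysis to test superiority of ADX-102 over vehicle is the stratified log-rank test, stratified for the baseline ACC grade". Sections 9.2.1 and 9.2.4 name it for both the log-rank test and the Cox model, and 9.2.5 names it for the CMH test. The two flare sections do not. Section 9.2.2 has "A log-rank test will be performed for between group comparison", and 9.2.3 repeats that sentence and adds "Cox proportional hazards model with treatment group as a factor will be used to estimate the hazard ratio".

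**The concern.** Section 9.2.4 uses nearly the same log-rank and Cox sentences as the flare sections, with the stratification phrase added. The phrase is missing from four sentences in a row of otherwise parallel text, and only for the two endpoints defined by flare rather than by cells or rescue. A reader could infer that stratification by cell grade was dropped for flare on purpose. Because Section 9 plans both versions of the log-rank test, the bare term in 9.2.2 does not by itself say which is meant.

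If that reading were right, two of the five secondary endpoints would be led by an unstratified p-value and hazard ratio. Were ACC grade prognostic for flare, the unstratified test would be somewhat conservative and less powerful. Its hazard ratio would be a marginal quantity lying nearer 1. With both tests planned and the lead unclear, there would also be room to choose between them after unmasking.

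**Working it through.** **1. The plan's own figure.** The only design calculation is for the primary endpoint (SAP 2.3.6). Inputs: hazards 0.2672 and 0.1098, about 53% censoring, two-sided alpha 0.05, 1:1 allocation. The hazard ratio is 0.2672 / 0.1098 = 2.434, with natural log 0.889. Schoenfeld power is Φ(½ √d × ln HR − 1.96), where d is the number of events.

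- N = 90: d = 0.47 × 90 = 42.3; ½ × 6.504 × 0.889 − 1.96 = 0.93; power 82.4% (SAP: 82%).
- N = 120: d = 0.47 × 120 = 56.4; ½ × 7.510 × 0.889 − 1.96 = 1.38; power 91.6% (SAP: 91%).

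Both reproduce. Neither involves a flare endpoint, so the point cannot affect them.

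**2. The text side by side.**

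| SAP section | Test | Cox model |
|---|---|---|
| 3.2.1 (general) | stratified log-rank | stratified |
| 9 (general) | both log-rank tests; stratified is primary | named, strata not repeated |
| 9.1 | log-rank, stratum named | stratum named |
| 9.2.1 | log-rank, stratum named | stratum named |
| 9.2.2 (flare) | log-rank, not stated | not stated |
| 9.2.3 (flare) | log-rank, not stated | not stated |
| 9.2.4 | log-rank, stratum named | stratum named |
| 9.2.5 | CMH, stratum named | n/a |

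**3. Does silence override the general rules?**

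- The flare endpoints are listed in 2.2.1.2 as secondary efficacy endpoints and are times to an event, so 3.2.1 and Section 9 both apply to them.
- The flare wording is incomplete, not incompatible. A stratified log-rank test is a log-rank test, and a stratified Cox model still has treatment as its factor. Section 9.2.4 describes its Cox model in those terms and then adds the stratum.
- Where the SAP wants an unstratified analysis it says so: the first sensitivity analysis in 9.1 is labelled unstratified, with an unadjusted hazard ratio.
- Where a section departs from a general rule it also says so: 9.2.5 and 9.3.4 each state that the visit-window assignment does not apply.
- Section 11 lists two changes from the protocol's analyses, both to population definitions. It has no flare exception.

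Read together, the stratified flare result leads, the unstratified log-rank test supports it, and the Cox model is stratified.

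**4. What a misreading could cost.** The documents give no flare event rate, flare hazard ratio, stratum mix or prognostic strength, so every input here is an assumption. Set-up: 60 per arm; grades 1+/2+/3+ at 50/35/15%; exponential event times seen at Days 4, 8, 15, 22 and 29; non-events censored at Week 4; no dropout; overall censoring 53%, borrowed from the primary endpoint; 100,000 simulated trials per scenario. Power is given as unstratified / stratified; discordance is the share of trials in which exactly one of the two tests has p < 0.05.

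| Hazard factor per ACC grade | Power, HR 2.43 | Power, HR 2.0 | Discordance, HR 2.43 | Discordance, HR 2.0 |
|---|---|---|---|---|
| 1.0 (not prognostic) | 90.9 / 90.7% | 73.2 / 73.0% | 0.9% | 1.7% |
| 0.8 | 90.7 / 90.7% | 72.7 / 72.9% | 1.0% | 1.9% |
| 0.6 | 89.7 / 90.8% | 70.6 / 72.8% | 1.7% | 3.3% |
| 0.4 | 87.1 / 91.1% | 66.0 / 73.2% | 4.2% | 7.7% |

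The last row assumes a 1 / 0.4² = 6.25-fold hazard difference between grades 1+ and 3+, for which the documents offer no support. Equal thirds across the grades widen the gap in that row to as much as 11.6 points, and keep it at 0.5 points or less in the first two rows. With no treatment effect, the unstratified test rejects in 3.7 to 5.1% of trials and the stratified test in 4.9 to 5.1%, so false positives are not inflated either way. Agreement with the SAP's 91% at HR 2.43 checks the set-up only, since the same inputs were supplied; it says nothing about flare.

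**The case for a change.** The best case for acting is that specific text normally governs general text, and that the omission follows a pattern. Section 9 states no precedence over the endpoint sections. One of its other general statements, that endpoints beyond the primary and secondary get no treatment comparison, is departed from by the mixed model in 9.3.1 and the t-test in 9.3.4. Its Cox sentence names no strata, and 3.2.1 calls for a stratified Cox model without ranking it. Adding a few words before unmasking would cost almost nothing and would remove any room for choice.

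Part of this stands. The drafting is uneven, and a programmer working from 9.2.2 or 9.2.3 alone could omit the stratum. But specific text overrides general text only where the two conflict, and here they do not. The mixed model and the t-test are positive specifications, and 9.3 expressly allows for them; silence is not a specification. The ranking sentence in Section 9 carries no such exception. Running only an unstratified flare test would itself breach Section 9, which requires both. The room for a later choice is closed by the ranking already on record, and 3.2.1 is the only place that speaks to stratifying the Cox model across time-to-event endpoints. A revision would repeat an existing rule.

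**Conclusion.** The concern does not hold as a defect in the analysis. Two subsections fail to repeat a rule that binding general sections state, and analysts following the whole SAP will fill the gap correctly. The effect on the flare results is nil when the plan is followed.

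This rests on reading 3.2.1 and Section 9 as applying to every time-to-event efficacy endpoint, which their wording supports and nothing contradicts. No power gain should be claimed for an edit: the simulated differences describe a misreading of the plan, and their flare inputs are all assumed. The endpoints are secondary, and SAP 3.2.3 rests the primary inference on a single endpoint without multiplicity adjustment. No change follows.

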#### 2.3.6. Sample Size and Power

Based on the Phase 2 clinical trial results, a true hazard rate of 0.2672 and 0.1098 is assumed for the time to treatment success in ADX-102 and vehicle group, respectively. With approximately 53% censoring rate, a sample size of 90 subjects (45 per group) yields 82% power to detect the superiority of ADX-102 over vehicle group with the use of a 2-sided log-rank test and a type I error of 0.05. Under the same assumption, a sample size of 120 subjects (60 per group) will provides 91% power.

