# 9.3.1. Slit Lamp External Eye Exam and Biomicroscopy

The examination of anterior uveitis is performed on both eyes (study and non-study eye) by external examination and biomicroscopy using a slit lamp. Slit lamp examination will be completed at Day 1 (Screening), Day 4, Week 1, Week 2, Week 3 and Week 4.

Changes from baseline in signs and symptoms of anterior uveitis which include Anterior Chamber Cell Grade, Anterior Chamber Flare Grade, Limbal Injection, Hypopyon, Peripheral Anterior Synechiae, Posterior Synechiae, Keratic Precipitates and Eyelid are the interest of treatment efficacy.

Descriptive summaries of the observed exam results at each scheduled visit as well as the change from baseline at each post-baseline visit will be presented for both eyes (study and non-study eye), without imputation. The numerical value of the exam result categories will be used in the summaries. The higher score representing more severe symptoms.

Number and percentage of subjects with Eyelid categories of Normal or Abnormal as well as the categorical shift from baseline at each post-baseline visit will also be summarized. The percentages will be calculated based on the number of subjects at each visit in each treatment group of the ITT analysis set. The percentages on the shift will be calculated based on the number of subjects with both baseline and post-baseline values.

In addition to the descriptive summary, the change from baseline in anterior chamber cell grade and flare grade will be analyzed using Mixed effect Model Repeat Measurement (MMRM) method. The MMRM model will include the fixed categorical effects of treatment, random effect visit, and treatment-by-visit interaction, as well as continuous fixed covariates of baseline score. An unstructured covariance structure of random effect will be used for modeling the within-subject errors. If the unstructured covariance structure matrix results in a lack of convergence, the model will be fit using covariance matrices of the following order until convergence is met:

- Heterogeneous Toeplitz
- Heterogeneous First-order autoregressive
- Toeplitz
- First-order autoregressive

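### The time-to-flare-success comparison (SAP 9.2.2) makes no use of baseline flare grade, a collected and probably prognostic value, and so may give up power on a secondary endpoint

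*SAP*

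**What the plan says.** SAP 9.2.2 defines flare treatment success as flare grade 0, reached and held to Week 4 without rescue. It names a log-rank test with no stratification and a Cox model with treatment as the only term: "Cox proportional hazards model with treatment group as a factor will be used to estimate the hazard ratio and corresponding 95% confidence interval". SAP 9.2.3 (Time to Flare Grade Reduction) uses the same form: "Cox proportional hazards model with treatment group as a factor will be used".

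SAP 9 sets a general rule for time-to-event endpoints: "The stratified analysis based on the baseline ACC grade used for randomization stratification will be the primary method". SAP 3.2.1 says the same. Sections 9.1, 9.2.1 and 9.2.4 repeat the ACC stratification. Sections 9.2.2 and 9.2.3 do not.

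SAP 9.3.1 schedules the slit lamp examination, which includes flare grade, at Day 1 and every later clinic visit. Its repeated-measures model for change in cell and flare grade includes "continuous fixed covariates of baseline score".

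Randomization is stratified by ACC grade only (SAP 2.3.5). Eligibility sets an ACC range but no minimum flare grade (Protocol 6.1).

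**The concern.** Success in 9.2.2 is a fixed target, grade 0. An eye starting at a high flare grade has further to go than one starting at a low grade, so starting grade is likely to predict time to success. If it does, a log-rank test or Cox model that ignores it has less power than one that uses it. ACC grade is at best a partial stand-in for flare.

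At stake is the chance of detecting a real flare effect on a listed secondary endpoint that carries a between-arm test. The adjustment needs no new data, and the SAP already makes it in its other flare model.

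**Working it through.** **Inputs from the SAP (2.3.6).** The only effect size given is for the primary cell endpoint: "a true hazard rate of 0.2672 and 0.1098 is assumed for the time to treatment success", a ratio of 0.2672/0.1098 = 2.4335. The stated power is "With approximately 53% censoring rate, a sample size of 90 subjects (45 per group) yields 82% power", "with the use of a 2-sided log-rank test and a type I error of 0.05"; also "a sample size of 120 subjects (60 per group) will provides 91% power". Nothing is given for flare: no distribution, event rate, effect or power.

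**Reproducing the stated power.** Schoenfeld: power = Φ(√(D/4) × ln HR − 1.96), with D = 0.47 × N and ln 2.4335 = 0.889.
- N = 90: D = 42.3; √10.575 × 0.889 − 1.96 = 0.93; power 82.4% (stated 82%).
- N = 120: D = 56.4; √14.1 × 0.889 − 1.96 = 1.38; power 91.6% (stated 91%).

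**Simulation 1: flare strata.** The assumptions are 120 subjects, five visits, about 47% events and a true hazard ratio of 2.43 within flare grade (borrowed from the primary endpoint). The latent ACC–flare correlation is 0.4, and no eye starts at grade 0. There were 2,000 trials per row, so the Monte Carlo error is about √(0.9 × 0.1/2000) = 0.7 point. Flare has three levels (35/45/20%) or four (15/30/35/20%), and each higher grade multiplies the success hazard by m. Loss is the flare-stratified power minus the unstratified power.

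| Levels | m | Unstratified | ACC strata | Flare strata | Loss (points) | Median HR, unstratified / flare strata |
|---|---|---|---|---|---|---|
| 3 | 1.0 | 91.6% | 91.4% | 91.0% | −0.6 | 2.47 / 2.46 |
| 3 | 0.7 | 90.8% | 90.9% | 91.4% | 0.6 | 2.42 / 2.45 |
| 3 | 0.5 | 87.6% | 87.6% | 91.6% | 4.0 | 2.31 / 2.43 |
| 3 | 0.33 | 81.0% | 81.8% | 91.7% | 10.7 | 2.13 / 2.43 |
| 4 | 1.0 | 91.6% | 91.4% | 91.0% | −0.6 | 2.47 / 2.45 |
| 4 | 0.7 | 91.0% | 91.0% | 91.6% | 0.6 | 2.38 / 2.44 |
| 4 | 0.5 | 84.7% | 85.0% | 91.4% | 6.7 | 2.17 / 2.43 |
| 4 | 0.33 | 68.1% | 69.8% | 89.6% | 21.5 | 1.91 / 2.38 |

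ACC stratification recovers at most 1.7 points (69.8 − 68.1), so applying the general rule of SAP 9 does not replace baseline flare. In 4,000 null trials at m = 0.5, type I error was 5.35% unstratified, 5.45% with ACC strata and 5.4% with flare strata.

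**Simulation 2: flare as a numeric covariate in an ACC-stratified Cox model.** The assumptions are 60 per arm, flare grades 1 to 3, exams at Days 4, 8, 15, 22 and 29, a vehicle hazard of 0.11 per week at flare grade 2, and 2,500 trials per row. Power without and then with flare at hazard ratio 2.43:
- m = 0.6: 92.8% to 94.6% (+1.8)
- m = 0.5: 92.7% to 95.0% (+2.3)
- m = 0.4: 89.7% to 95.0% (+5.3)
- m = 0.3: 84.0% to 95.8% (+11.8)

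At hazard ratio 2.0 the gains are larger: 69.6% to 79.2% (+9.6) at m = 0.4. Type I error was 4.7%.

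**Eyes already at flare 0.** Suppose 20% start at grade 0, 80% of those stay there and count as events at the first visit, and the other grades are not prognostic. Power for flare success is then 70.0% unstratified and 78.8% with flare strata, but the median hazard ratio is 1.85 against 1.87. Adjustment recovers some power and leaves the hazard ratio diluted.

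**The case against.** **No rule of the plan is broken.** A reader might infer that the SAP adjusts each endpoint for its own baseline and forgot flare. The documents do not support that. SAP 3.2.1 and 9 stratify by the randomization factor, and Time to Rescue (9.2.4), which is not a cell outcome, is also ACC-stratified. This objection stands: leaving baseline flare out is a choice that costs efficiency. The textual inconsistency is a different one, that 9.2.2 and 9.2.3 do not repeat the ACC stratum.

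**The hazard ratio is not biased.** The lower unadjusted ratios in the table might be read as bias toward 1. They reflect non-collapsibility: the marginal ratio and the ratio conditional on flare are different quantities, and both are valid. This stands.

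**Chance imbalance does not threaten validity.** A reader might infer that, because only ACC is balanced by design, an uneven split of baseline flare would invalidate the comparison. The test's error rate already covers chance imbalance, and simulated type I error is unaffected. This stands.

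**It does not carry over to 9.2.3.** There the event is a one-grade fall from the subject's own baseline, so every eye at 1+ or more has the same distance to go. Neither simulation models that event among such eyes. This stands.

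**The size is assumed.** The larger gains need steep gradients. With three levels, m = 0.5 means a 4-fold difference in hazard between the lowest and highest grade (1/0.5²), and m = 0.33 about 9-fold (1/0.33²). The stakes are also limited: these are secondary endpoints with no stated power, and 9.3.1 already plans a baseline-adjusted flare analysis. All of this limits the weight of the point. It gives no reason to leave out a collected covariate that costs almost nothing.

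**Conclusion.** The point holds for SAP 9.2.2 as a probable, avoidable loss of power. Under either reading of the stratification rule, baseline flare is not used. The loss is nil if flare is not prognostic and under 1 point at m = 0.7, which is within simulation error. It is about 4 to 7 points at m = 0.5 (2.3 points under the second set of assumptions) and 10.7 to 21.5 points at m = 0.33.

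These figures rest on the primary endpoint's hazard ratio and on assumed flare distributions and gradients. That starting grade is prognostic at all is an inference from the endpoint definition, not a figure in the documents.

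The planned test is valid, its hazard ratio is a valid marginal estimate, and the primary result is not touched. No gain has been shown for 9.2.3 among eyes with flare of 1+ or more.

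**What to change.** Before unmasking, revise SAP 9.2.2 as follows:

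- Make the between-arm comparison the score test for treatment from a Cox model stratified by randomization ACC grade, with treatment and study-eye baseline flare grade as terms.
- Enter flare as a categorical factor, pooling sparse grades and keeping grade 0 as its own level. A single linear term cannot represent eyes that already meet the target. Fix the pooling rule from masked data.
- Report the hazard ratio and 95% CI from this model, labelled as conditional on baseline flare.
- Keep the ACC-stratified log-rank test as supportive. This also brings 9.2.2 into line with SAP 3.2.1 and 9.

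The same adjustment may be used in 9.2.3 for consistency, without claiming a gain. State separately how eyes at flare 0 at baseline are handled in both sections, since adjustment alone does not settle that.

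The cost is SAP wording and one covariate from the Day 1 examination. The test becomes model-based, the hazard ratio changes meaning, and the gain may be negligible. The simulations used flare strata and a numeric term; this exact categorical model was not itself simulated.
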